2. MMRM: Continuous variables such as EASI and SCORAD scores will be assumed to be missing after rescue or discontinuation and then an MMRM analysis will be performed. An additional analysis will be performed that includes all available data whether rescue medication was given or not.
3. Last observed carried forward (LOCF): An additional analysis will be performed that uses the last observed value on or prior to discontinuation or rescue therapy. This will

then be analyzed using a logistic model for categorical variables or ANCOVA for continuous variables as described above.

Additional sensitivity analyses for the primary and key secondary endpoints such as tipping point analyses as well as a reference based multiple imputation method may be done and will be specified in the SAP.

Adjustment for Multiple Comparisons:

Multiplicity controlled analyses will be performed on the primary and major secondary endpoints to control the overall family-wise Type I error rate at a 2-sided α level of 0.05. The graphical multiple testing procedure described in Bretz et al. (2011) will be used. The graphical approach is a closed testing procedure; hence it strongly controls the family-wise error rate across all endpoints (Alosh et al. 2014). Details of the specific graphical testing scheme (including testing order, interrelationships, Type I error allocation, and the associated propagation) will be prespecified in the SAP.

The following is a list of primary and key secondary endpoints to be tested:

Primary:

- proportion of baricitinib 4-mg patients achieving IGA of 0 or 1 and ≥ 2 -point improvement from baseline at Week 16.
- proportion of baricitinib 2-mg patients achieving IGA of 0 or 1 and ≥ 2 -point improvement from baseline at Week 16.

Key Secondaries:

Evaluated for 2-mg and 4-mg:

- proportion of patients achieving EASI75 at 16 weeks
- proportion of patients achieving EASI90 at 16 weeks
- percent change from baseline in EASI score at 16 weeks
- proportion of patients achieving SCORAD75 at 16 weeks
- proportions of patients achieving a 4-point improvement in Itch NRS at 2 days, 1 week, 2 weeks, 4 weeks, and 16 weeks
- mean change from baseline in the score of Item 2 from the ADSS at 1 week and 16 weeks
- mean change from baseline in skin pain NRS at 16 weeks

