## 6. A Priori Statistical Methods

### 6.1. Determination of Sample Size

Study JAIY will aim to enroll approximately 300 patients  $\geq 18$  years of age. The proposed sample size will ensure a 89% power to detect an absolute difference of 20% between the baricitinib 4 mg and placebo treatment groups and the baricitinib 2 mg and placebo treatment groups, each using a 2-sided alpha of 0.025 and a Fisher's exact test, assuming a 10% placebo response rate for the primary endpoint. The assumptions are based on what was observed in the Phase 2 study (JAHG). The proposed end point of IGA 0 or 1 represents patients whose AD is clear or almost clear from a baseline of moderate or severe disease. The anticipated effect size represents 2 times more patients achieving this benefit compared to placebo, which, in discussion with therapeutic experts, is of a magnitude that is considered clinically relevant.

Sample size and power estimates were obtained from nQuery® Advisor 7.0.

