### 6.2. General Considerations

This plan describes *a priori* statistical analyses for efficacy, health outcomes, and safety that will be performed.

Statistical analysis of this study will be the responsibility of Eli Lilly and Company (Lilly). The statistical analyses will be performed using SAS® Version 9.4 or higher.

Not all displays described in this SAP will necessarily be included in the clinical study report (CSR). Not all displays will necessarily be created as a "static" display. Some may be incorporated into interactive display tools instead of or in addition to a static display. Any display described in this SAP and not included in the CSR will be available upon request.

Statistical tests of treatment effects and confidence intervals (CIs) will be performed at a 2-sided significance level of 0.05, unless otherwise stated (e.g., graphical multiple testing strategy in Section 6.6).

Data collected at ETVs will be mapped to the closest scheduled visit number for that patient if it falls within the visit window as discussed in Section 6.2.2. For by-visit summaries, only visits in which a measure was scheduled to be collected will be summarized. Any unscheduled visit data will be included at the patient-level listings. However, the data will still be used in other analyses, including shift analyses for safety analytes, change from baseline using modified last observation carried forward (mLOCF) for efficacy analyses, and other categorical analyses including safety.

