#### **6.4.5. Tipping Point Analyses**

To investigate the missing data mechanism, sensitivity analyses using multiple imputation (MI) under the missing not at random assumption will be provided for the following primary and key secondary objectives as given in [Table JAIY.6.3](#).

All patients in the ITT population will be included. Data after the occurrence of intercurrent events (after application of the primary censoring rule) will be set to missing.

Within each analysis, a most extreme case will be considered, in which all missing data for patients randomized to baricitinib 2 mg or 4 mg will be imputed using the worst possible result and all missing data for patients randomized to placebo will be imputed with the best possible result. Treatment differences will be analyzed using logistic regression or ANCOVA (Section [6.1](#)) as appropriate.

For continuous variables, the following process will be used to determine the tipping point:

1. To handle intermittent missing visit data, a Markov chain Monte Carlo method (SAS® Proc MI with MCMC option) will be used to create a monotone missing pattern.
2. A set of Bayesian regressions (using SAS® Proc MI with MONOTONE option) will be used for the imputation of monotone dropouts. Starting from the first visit with at least 1 missing value, the regression models will be fit sequentially with treatment as a fixed effect and values from the previous visits as covariates.

3. A delta score is added to all imputed scores at the primary time point for patients in the baricitinib treatment groups, thus worsening the imputed value. The delta score is capped for patients based on the range of the outcome measure being analyzed.
4. Treatment differences between baricitinib and placebo are analyzed for each imputed dataset using ANCOVA (Section 6.1). Results across the imputed datasets are aggregated using SAS® Proc MIANALYZE in order to compute a p-value for the treatment comparisons for the given delta value.
5. Steps 3 and 4 are repeated, and the delta value added to the imputed baricitinib scores is gradually increased. The tipping point is identified as the delta value which leads to a loss of statistical significance (aggregated p-value >0.05) when evaluating baricitinib relative to the placebo group.

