As a reference, for each delta value used in Steps 3 through 5, a fixed selection of delta values (ranging from slightly negative to slightly positive) will be added to imputed values in the placebo group, and Step 4 will be performed for the combination. This will result in a 2-d table, with the columns representing the delta values added to the imputed placebo responses, and the rows representing the delta values added to the imputed baricitinib responses. Separate 2-d tables will compare each baricitinib dose group to placebo.

A similar process will be used for the categorical variables:

1. Missing responses in the baricitinib groups will be imputed with a range of low response probabilities, including probabilities of 0, 0.1, and 0.2.
2. For missing responses in the placebo group, a range of response probabilities (for example, probability = 0, 0.2 ... 1) will be used to impute the missing values. Multiple imputed datasets will be generated for each response probability.
3. Treatment differences between baricitinib and placebo are analyzed for each imputed dataset using logistic regression (Section 6.1). Results across the imputed datasets are aggregated using SAS® Proc MIANALYZE in order to compute a p-value for the treatment comparisons for the given response probability. If the probability values do not allow for any variation between the multiple imputed datasets (for example, all missing responses in the placebo and baricitinib groups are imputed as responders and nonresponders, respectively), then the p-value from the single imputed dataset will be used.

The tipping point is identified as the response probability value within the placebo group that leads to a loss of statistical significance when evaluating baricitinib relative to placebo.

For tipping point analyses the number of imputed data sets will be  $m=100$  and the seed values to start the pseudorandom number generator of SAS Proc MI (same values for MCMC option and for MONOTONE option) are given in [Table JAIY.6.3](#).

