## 6.6. Multiple Comparisons/Multiplicity

The primary and key secondary endpoints will be adjusted for multiplicity in order to control the overall family-wise Type I error rate at a 2-sided alpha level of 0.05.

The following is a list of primary and key secondary endpoints to be tested.

Primary Null Hypotheses:

[figure not shown]
- Null Hypotheses[IGA0-1]: Proportion of baricitinib 4-mg patients achieving IGA of 0 or 1 with a  $\geq 2$ -point improvement from baseline at Week 16 is equal to the proportion of placebo patients achieving IGA of 0 or 1 with a  $\geq 2$ -point improvement from baseline at Week 16
- Null Hypotheses[IGA0-1]: Proportion of baricitinib 2-mg patients achieving IGA of 0 or 1 with a  $\geq 2$ -point improvement from baseline at Week 16 is equal to the proportion of placebo patients achieving IGA of 0 or 1 with a  $\geq 2$ -point improvement from baseline at Week 16

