**Figure JAIY.6.1. Illustration of graphical multiple testing procedure with initial  $\alpha$  allocation and weights.**

For Japan, the same testing strategy will be used, however, the proportion of patients achieving EASI75 and IGA of 0 or 1 at Week 16 are considered co-primary. Both endpoints have to meet statistical significance compared with placebo in order to demonstrate a superiority of a given baricitinib dose (baricitinib 4-mg and/or baricitinib 2-mg) compared with placebo.

There will be no adjustment for multiple comparisons for any other analyses.

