		
 
▪ Change from baseline in SCORAD score
 
▪ Percent change from baseline in SCORAD score
 
	Change from baseline: observed SCORAD score – baseline SCORAD score  % change from baseline: $100 \times \frac{Observed\ score - Baseline}{Baseline}$	Missing if baseline or observed value is missing.
		SCORAD75	% Improvement in SCORAD from baseline $\geq 75\%$ : % change from baseline $\leq -75$	Missing if baseline or observed value is missing.
		SCORAD90	% Improvement in SCORAD from baseline $\geq 90\%$ : % change from baseline $\leq -90$	Missing if baseline or observed value is missing.

Table JAIY.6.5. Description of Primary, Secondary and Exploratory Efficacy Analyses

Measure	Variable	Analysis Method (Section 6.2.3)	Population (Section 6.2.1)	Comparison/Time Point	Analysis Type
Validated Investigator's Global Assessment for AD (IGA)	Proportion of patients achieving IGA [0,1] with a $\geq 2$ -point improvement	Logistic regression using NRI	ITT	Bari 4 mg or Bari 2 mg vs PBO; Week 16	Primary analysis
			PPS	Bari 4 mg or Bari 2 mg vs PBO; Week 16	Sensitivity analysis
			ITT	Bari 4 mg or Bari 2 mg vs PBO; Week 4	Secondary analysis
		Logistic regression using pMI and Tipping Point	ITT	Bari 4 mg or Bari 2 mg vs PBO; Week 16	Sensitivity analysis
	Proportion of patients achieving IGA [0]	Logistic regression using NRI	ITT	Bari 4 mg or Bari 2 mg vs PBO; Week 16	Secondary analysis
Eczema Area and Severity Index (EASI)	
 
EASI score
 
Change from baseline in EASI score
 
Percent change from baseline in EASI score
 
	MMRM	ITT	Bari 4 mg or Bari 2 mg vs PBO; Week 16	Key secondary analysis
			PPS	Bari 4 mg or Bari 2 mg vs PBO; Week 16	Sensitivity analysis
		ANCOVA using mLOCF	ITT	Bari 4 mg or Bari 2 mg vs PBO; Week 16	Sensitivity analysis
		pMI and Tipping Point	ITT	Bari 4 mg or Bari 2 mg vs PBO; Week 16	Sensitivity analysis
	
 
Proportion of patients achieving EASI50
 
	Logistic regression using NRI	ITT	Bari 4 mg or Bari 2 mg vs PBO; Week 16	Secondary analysis
	
 
Proportion of patients achieving EASI75
 
Proportion of patients achieving EASI90
 
	Logistic regression using NRI	ITT	Bari 4 mg or Bari 2 mg vs PBO; Week 16	Key secondary analysis
			PPS	Bari 4 mg or Bari 2 mg vs PBO; Week 16	Sensitivity analysis

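### The tipping point uses p >0.05 for continuous variables and no stated level for categorical ones, so robustness is overstated for any hypothesis rejected at a local level below 0.05

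*SAP*

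**What the plan says.** SAP Section 6.4.5 plans tipping point analyses for primary and key secondary objectives. In the process for continuous variables, step 5 places the tip at the "delta value which leads to a loss of statistical significance (aggregated p-value >0.05"). The process for categorical variables places it at the "response probability value within the placebo group that leads to a loss of statistical significance" and gives no number.

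The hypotheses concerned belong to the multiplicity-controlled family. Section 6.6 sets out to "control the overall family-wise Type I error rate at a 2-sided alpha level of 0.05" and lists 26 null hypotheses: 2 primary, and 12 key secondary for each dose. Section 6.2 says that tests "will be performed at a 2-sided significance level of 0.05, unless otherwise stated (e.g., graphical multiple testing strategy in Section 6.6"), so it names the graph as an exception to the 0.05 default. The sample size section powers both dose comparisons, "each using a 2-sided alpha of 0.025". Protocol Section 10.3.1 leaves the details to the SAP: "Type I error allocation, and the associated propagation) will be prespecified in the SAP". They are in Figure JAIY.6.1, captioned "Illustration of graphical multiple testing procedure with initial" allocation and weights; the figure is not reproduced in the text reviewed.

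The tables differ on whether any continuous endpoint has a tipping point analysis. Table JAIY.6.3, to which Section 6.4.5 refers, lists binary endpoints only. Table JAIY.6.1 assigns the continuous key secondaries MMRM, mLOCF and pMI. Table JAIY.6.5 lists "pMI and Tipping Point" in the row that includes percent change in EASI.

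**The concern.** A tipping point shows how adverse the missing data would have to be before the conclusion fails. For a hypothesis in the graph, the conclusion is rejection at its local level. Two doses and 26 hypotheses share 0.05, so a local level reaches 0.05 only when all the alpha has passed to that hypothesis. A fixed 0.05 cut is therefore either exact or too lenient, and never too strict.

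Where it is too lenient, the report would describe a result as robust to a shift at which its controlled claim has already gone. In the clearest case, a result tested at 0.025 with p between 0.025 and 0.05 would receive a positive tipping delta for a claim that it never had.

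**Working it through.** **1. The plan's own figure.** Inputs from SAP Sections 5.1 and 6.1: 100 per arm, 10% v 30% response, two-sided Fisher exact test. Full binomial enumeration gives power of 89.1% at alpha 0.025 and 93.5% at alpha 0.05. The stated 89% therefore rests on 0.025 per dose, and 0.025 + 0.025 = 0.05 uses the whole family-wise level.

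**2. Continuous variables.** Assume that the pooled difference falls linearly in delta with a roughly constant standard error. Let Z be the test statistic before any shift, SE its standard error, and f the imputed share of the baricitinib arm. Then

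tipping delta = (Z − z_crit) × SE / f.

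The critical values are 1.960 at 0.05 and 2.241 at 0.025. The 0.05 rule puts the tip 0.281 × SE / f later, and the ratio of the two deltas does not depend on SE or f:

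| Z | Z − 1.960 | Z − 2.241 | Ratio |
|---|---|---|---|
| 4 | 2.040 | 1.759 | 1.16 |
| 3 | 1.040 | 0.759 | 1.37 |

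The ratio grows without bound as Z falls to 2.241, so values near that limit say little. With a local level of 0.05 the ratio is 1.

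**3. Primary endpoint, if a 0.05 cut were used.** Assumptions, not document figures: observed responders of 30 or 25 on baricitinib v 10 on placebo, out of 100 per arm; 15 placebo patients missing; missing baricitinib patients counted as nonresponders; unadjusted log odds ratio. Missing placebo responses are imputed with probability q. With m = 100 imputations, Rubin's rules give a total variance of W + (1 + 1/100) × B, where W is the mean within-imputation variance and B the between-imputation variance.

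- At q = 0 with 30 v 10: log odds ratio = ln[(30 × 90)/(70 × 10)] = 1.350; variance = 1/30 + 1/70 + 1/10 + 1/90 = 0.1587; z = 3.39.
- At q = 0.37: mean log odds ratio 0.852, W = 0.1247, B = 0.0206; total variance = 0.1247 + 1.01 × 0.0206 = 0.1455; z = 0.852/0.381 = 2.23, p about 0.025.
- At q = 0.48: mean log odds ratio 0.730, W = 0.1186, B = 0.0189; total variance = 0.1377; z = 0.730/0.371 = 1.97, p about 0.05.

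| Responders | Tip at 0.05 | Tip at 0.025 |
|---|---|---|
| 30 v 10 | 0.48 | 0.37 |
| 25 v 10 | 0.22 | 0.13 |

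The gap is about 0.1. On the SAP's example grid of 0, 0.2, ... 1, it moves the reported tip by one step: 0.6 instead of 0.4 in the first case, 0.4 instead of 0.2 in the second.

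**The case against.** The strongest reply is that the numeric rule reaches little. It is written only for continuous variables. By Tables JAIY.6.1 and 6.3 no continuous endpoint has a tipping point analysis, and only the EASI row of Table JAIY.6.5 brings the rule into use. That stands, and it is why the tables need reconciling.

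A reader might infer that the SAP sets the primary endpoint's tipping point at 0.05. It does not. The categorical text gives no number, and Section 6.2 exempts the graph from the 0.05 default, so that text could be read as meaning the graph's level. It is open rather than wrong. A programmer could still carry over 0.05, the only number that Section 6.4.5 attaches to losing significance.

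A reader might also take 0.025 as the graph's starting level. The documents support that only indirectly: 0.025 comes from the power statement for the binary primary endpoint, it matches the protocol's figure, and the SAP revision history says that the graph was updated in Version 2. The figure that would settle it is not reproduced in the text reviewed, which is not a gap in the plan.

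Finally, the SAP plans a two-way table of delta values for each dose and a most-extreme case. If the p-values are displayed, a reader can apply another threshold. That softens the problem, but the headline tip would still be the one at 0.05.

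**Conclusion.** The concern holds in conditional form. The continuous rule is not tied to the level at which the hypothesis was tested, and the categorical rule names no level. The first can only err towards overstated robustness; the second permits the same error. It occurs for hypotheses rejected at a local level below 0.05 and vanishes for those that have reached 0.05 by propagation. A blanket statement that the plan overstates robustness would go further than the documents allow.

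The sizes above rest on an assumed local level of 0.025. The continuous figures also need a linear shift with constant standard error, which the SAP's cap on delta at the range of the scale can break. The binary figures also depend on the assumed response and missing counts. The primary tests and the family-wise error control are unchanged.

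**What to change.** In Section 6.4.5, replace the fixed threshold in step 5 and complete the categorical rule with one definition: the tipping point is the smallest shift (continuous) or placebo response probability (categorical) at which the aggregated p-value exceeds the local significance level at which that hypothesis was rejected in the graphical procedure of Section 6.6. Take that level from the main analysis and report it beside the tip. A hypothesis that was not rejected has no claim to tip. The tip at 0.05 may be shown alongside, labelled as descriptive.

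Reconcile Tables JAIY.6.1 and 6.3 with Table JAIY.6.5: either drop the continuous EASI tipping point from Table 6.5, or add it to Table 6.1 and give it an entry and seed in Table 6.3.

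The cost is a few phrases in the SAP and a table entry, with no new data or design change. Some reported tipping points may be slightly less favourable.

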**Table JAIY.6.3. Seed Values for Imputation**

Analysis	Seed value
Proportion of patients achieving IGA (0,1) with $\geq 2$ -point improvement at Week 16; primary censoring rule	123470
Proportion of patients achieving EASI75 at Week 16; primary censoring rule Proportion of patients achieving EASI90 at Week 16; primary censoring rule	123471
Proportions of patients achieving a 4-point improvement from baseline in Itch NRS at Week 16, primary censoring rule	123472
Proportion of patients achieving SCORAD75 at Week 16; primary censoring rule	123473

## 6.5. Multicenter Studies

This study will be conducted by multiple investigators at multiple sites internationally. The countries will be categorized into geographic regions, as described in Section 5.2.

For the analysis of the primary endpoint, treatment-by-region interaction will be added to the logistic regression model as a sensitivity analysis and results from this model will be compared to the primary model (without the interaction effect). If the treatment-by-region interaction is significant at a 2-sided  $\alpha$  level of 0.1, the nature of this interaction will be inspected as to whether it is quantitative (i.e., the treatment effect is consistent in direction across all regions but not in size of treatment effect) or qualitative (the treatment is beneficial in some but not all regions). If the treatment-by-region interaction effect is found to be quantitative, results from the primary model will be presented. If the treatment-by-region interaction effect is found to be qualitative, further inspection will be used to identify in which regions baricitinib is found to be more beneficial.

## 6.6. Multiple Comparisons/Multiplicity

The primary and key secondary endpoints will be adjusted for multiplicity in order to control the overall family-wise Type I error rate at a 2-sided alpha level of 0.05.

The following is a list of primary and key secondary endpoints to be tested.

Primary Null Hypotheses:

[figure not shown]
- Null Hypotheses[IGA0-1]: Proportion of baricitinib 4-mg patients achieving IGA of 0 or 1 with a  $\geq 2$ -point improvement from baseline at Week 16 is equal to the proportion of placebo patients achieving IGA of 0 or 1 with a  $\geq 2$ -point improvement from baseline at Week 16
- Null Hypotheses[IGA0-1]: Proportion of baricitinib 2-mg patients achieving IGA of 0 or 1 with a  $\geq 2$ -point improvement from baseline at Week 16 is equal to the proportion of placebo patients achieving IGA of 0 or 1 with a  $\geq 2$ -point improvement from baseline at Week 16

## Key Secondary Null Hypotheses:

- Null Hypotheses[EASI75]: Proportion of baricitinib 4-mg patients achieving EASI75 is equal to the proportion of placebo patients achieving EASI75 at Week 16
- Null Hypotheses[ITCH W16]: Proportion of baricitinib 4-mg patients achieving a 4-point improvement in Itch NRS is equal to the proportion of placebo patients achieving a 4-point improvement in Itch NRS at Week 16 among patients with baseline Itch NRS score  $\geq 4$
- Null Hypotheses[EASI PCFB]: Percent change from baseline in EASI score for baricitinib 4-mg patients is equal to the percent change from baseline in EASI score for placebo patients at Week 16
- Null Hypotheses[ITCH W4]: Proportion of baricitinib 4-mg patients achieving a 4-point improvement in Itch NRS is equal to the proportion of placebo patients achieving a 4-point improvement in Itch NRS at Week 4 among patients with baseline Itch NRS score  $\geq 4$
- Null Hypotheses[SCORAD75]: Proportion of baricitinib 4-mg patients achieving SCORAD75 is equal to the proportion of placebo patients achieving SCORAD75 at Week 16
- Null Hypotheses[EASI 90]: Proportion of baricitinib 4-mg patients achieving EASI90 is equal to the proportion of placebo patients achieving EASI90 at Week 16
- Null Hypotheses[PAIN NRS]: Mean change from baseline in Skin Pain NRS for baricitinib 4-mg patients is equal to the mean change from baseline in Skin Pain NRS for placebo patients at Week 16
- Null Hypotheses[ADSS2 W16]: Mean change from baseline in the score of Item 2 of the ADSS for baricitinib 4-mg patients equal to the mean change from baseline in the score of Item 2 of the ADSS for placebo patients at Week 16
- Null Hypotheses[ITCH W2]: Proportion of baricitinib 4-mg patients achieving a 4-point improvement in Itch NRS is equal to the proportion of placebo patients achieving a 4-point improvement in Itch NRS at Week 2 among patients with baseline Itch NRS score  $\geq 4$
- Null Hypotheses[ADSS2 W1]: Mean change from baseline in the score of Item 2 of the ADSS for baricitinib 4-mg patients is equal to the mean change from baseline in the score of Item 2 of the ADSS for placebo patients at Week 1
- Null Hypotheses[ITCH W1]: Proportion of baricitinib 4-mg patients achieving a 4-point improvement in Itch NRS is equal to the proportion of placebo patients achieving a 4-point improvement in Itch NRS at Week 1 among patients with baseline Itch NRS score  $\geq 4$
- Null Hypotheses[ITCH D2]: Proportion of baricitinib 4-mg patients achieving a 4-point improvement in Itch NRS is equal to the proportion of placebo patients achieving a 4-point improvement in Itch NRS at Day 2 among patients with baseline Itch NRS score  $\geq 4$
- Null Hypotheses[EASI75]: Proportion of baricitinib 2-mg patients achieving EASI75 is equal to the proportion of placebo patients achieving EASI75 at Week 16
- Null Hypotheses[ITCH W16]: Proportion of baricitinib 2-mg patients achieving a 4-point improvement in Itch NRS is equal to the proportion of placebo patients achieving a 4-point improvement in Itch NRS at Week 16 among patients with baseline Itch NRS score  $\geq 4$

- Null Hypotheses[EASI PCFB]: Percent change from baseline in EASI score for baricitinib 2-mg patients is equal to the percent change from baseline in EASI score for placebo patients at Week 16
- Null Hypotheses[ITCH W4]: Proportion of baricitinib 2-mg patients achieving a 4-point improvement in Itch NRS is equal to the proportion of placebo patients achieving a 4-point improvement in Itch NRS at Week 4 among patients with baseline Itch NRS score  $\geq 4$
- Null Hypotheses[SCORAD75]: Proportion of baricitinib 2-mg patients achieving SCORAD75 is equal to the proportion of placebo patients achieving SCORAD75 at Week 16
- Null Hypotheses[EASI90]: Proportion of baricitinib 2-mg patients achieving EASI90 is equal to the proportion of placebo patients achieving EASI90 at Week 16
- Null Hypotheses[PAIN NRS]: Mean change from baseline in Skin Pain NRS for baricitinib 2-mg patients is equal to the mean change from baseline in Skin Pain NRS for placebo patients at Week 16
- Null Hypotheses[ADSS2 W16]: Mean change from baseline in the score of Item 2 of the ADSS for baricitinib 2-mg patients is equal to the mean change from baseline in the score of Item 2 of the ADSS for placebo patients at Week 16
- Null Hypotheses [ITCH W2]: Proportion of baricitinib 2-mg patients achieving a 4-point improvement in Itch NRS is equal to the proportion of placebo patients achieving a 4-point improvement in Itch NRS at Week 2 among patients with baseline Itch NRS score  $\geq 4$
- Null Hypotheses[ADSS2 W1]: Mean change from baseline in the score of Item 2 of the ADSS for baricitinib 2-mg patients is equal to the mean change from baseline in the score of Item 2 of the ADSS for placebo patients at Week 1
- Null Hypotheses[ITCH W1]: Proportion of baricitinib 2-mg patients achieving a 4-point improvement in Itch NRS is equal to the proportion of placebo patients achieving a 4-point improvement in Itch NRS at Week 1 among patients with baseline Itch NRS score  $\geq 4$
- Null Hypotheses[ITCH D2]: Proportion of baricitinib 2-mg patients achieving a 4-point improvement in Itch NRS is equal to the proportion of placebo patients achieving a 4-point improvement in Itch NRS at Day 2 among patients with baseline Itch NRS score  $\geq 4$

The multiple testing strategy for the primary and the major secondary endpoint will be implemented through the graphical testing procedure depicted by [Figure JAIY.6.1](#).

